**Extra Visits**

1. Extra visits (or in-person visits when phone visits are called for) will "kick in" if:
2. Patient reports on-going or intermittent negative effects, including but not limited to:
  - a. "Flash-backs"
  - b. Psychotic or quasi-psychotic (e.g., illusions, non-paranoid worries re. how others are viewing or treating them) experiences
3. Significant (e.g., > 25% increase in BDD-YBOCS) worsening from original severity.
4. Significant suicidality (e.g., patient reports suicidal thinking with any intent to act)
5. Physician's clinical judgment

**Detailed Procedure for Staff Escort Home**

In the event that it is deemed appropriate for a patient to return home following their psilocybin experience and said patient has not provided a responsible party to accompany him or her home, a staff member will accompany the individual from the BSU treatment room to the exterior door of their home. Transportation will be via a car service for which we will pay. The staff member will be instructed to contact the Anxiety Disorders Clinic doctor on call should he or she note grogginess or unsteady gait or other reasons to think the subject might have trouble being alone and the doctor will determine whether to have the staff member bring the subject back to NYSPI for further observation, erring on the side of further observation. Else, the staff member will allow the individual to enter their home and close the door, the staff member remaining outside and relieved of escort duties.

Table - Schedule of Study Procedures											
Visit	1	1a, 1b, 1c, etc.	2	3	4	5	6	7	8	9	10
Day	Screen Visit	Screening Period	-1	Psilo-cybin	+1	+7	+14	+21	+42	+63	+84
Informed Consent	X										
Medical History	X		X								
MINI Interview	X										
Documentation of Birth Control Method	X										
Prior/Concomitant Meds	X	X	X	X	X	X	X	X	X	X	X
Hamilton Rating Scale for Depression	X		X		x				x		X
Columbia Suicide Severity Rating Scale	X				x						x
BDD-Yale-Brown OCD Scale	X		X	X	X	X	X	X	X	X	X

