## Protocol Summary Form

Inclusion:	
1. Age 18-55	Date of birth
2. DSM-5- body dysmorphic disorder, non-delusional subtype, for >6 months by history. Non-delusional subtype will be operationalized by Brown Assessment of Beliefs Scale (BABS) 6-item total <18 (Phillips et al., 2006)	SCID -5 BDD module, BABS
3. At least moderate severity of BDD, operationalized by total score >24 on the Yale-Brown Obsessive-Compulsive Scale Modified for Body Dysmorphic Disorder (BDD-YBOCS),	BDD-YBOCS
4. At least moderate overall severity, operationalized by score of at least moderate (4 or greater) on the CGI severity scale	CGI severity scale
5. History of intolerance of, or nonresponse to, a prior adequate trial of an SSRI ( $\geq$ 2 months of fluoxetine 20 mg/day or equivalent), SNRI, or clomipramine	Psychiatric History
6. Currently in psychotherapy (other than CBT for BDD)	Psychiatric History
7. Able to provide informed consent	Psychiatric Assessment
Exclusion:	
1. Current major depressive disorder of greater than moderate severity (17-item Hamilton Rating Scale for Depression total >20)	Hamilton Rating Scale for Depression

2. Current or past DSM-5 bipolar disorder, psychotic disorder, or borderline personality disorder. First degree relative with psychotic disorder or bipolar I disorder.	MINI, family history
3. DSM-5 alcohol or drug use disorder in the past 3 months, or positive result on urine drug screen for illicit substance of abuse (except that prior cannabis use subthreshold for abuse diagnosis will be permitted if discontinued >24 hours prior to dosing)	MINI, urine drug screen
4. Current clinically significant suicidality or a suicide attempt within the past year	Psychiatric Assessment, MINI, CSSR (items 3 or 4 rated “yes” for active suicidal ideation)
5. Need for inpatient or partial hospital treatment	Psychiatric Assessment
6. Mental retardation, dementia, brain damage, or other cognitive impairment that would interfere with participation	Psychiatric Assessment and History
7. Body image concerns accounted for primarily by an eating disorder	Psychiatric Assessment
8. Body dysmorphic disorder criteria not met if weight concerns are excluded	Psychiatric Assessment

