chemistries including thyroid function. A physical examination will be performed at the screening or between screening and Visit 2 (Day -1), with results obtained before psilocybin administration day.

Additional screening will specifically assess eligibility for the MRI portion of the study with the self-rated PhenX Toolkit Hand Dominance Measure and MRI Metal Screening Questionnaire. Contraindications to MRI scanning are:

- Paramagnetic metallic implants or devices
- Contraindicating magnetic resonance imaging or any other non-removable paramagnetic metal in the body (e.g., pacemaker, paramagnetic metallic prosthesis, surgical clips, shrapnel, necessity for constant medicinal patch, some tattoos)
- Being unable to tolerate the scanning procedures (i.e., severe obesity, claustrophobia)

Patients with contraindicated metal or left-handedness will not be offered MRI participation but will complete all other parts of the protocol.

Additional visits (V1a, V1b) will be scheduled as needed to follow up on any lab abnormalities and for patient to establish relationship with study therapist.

Participants will be invited to bring to the screening a companion (friend/family member) whom they would like to support them through the study. Such a companion will be informed of their potential role and will be asked to sign a “caregiver” consent form at the Screening Visit. Caregivers will receive information about the signs of worsening of depression and suicide risk and ways to contact the study team if necessary. The caregiver will complete a questionnaire at screening, Week 3 and Week 12.

**2. Visit 2 (Baseline, Day -1).** Eligibility and willingness to participate will be reassessed. At this visit, the patient meets with the therapist who describes what the experience might be like and how the therapist will handle any difficulties the patient may have with the experience. MRI-eligible subjects will complete acquisition of resting state fMRI. Subjects will also complete an inverted face computer task in which they will view an image of a face and then will be shown an image of two faces (one matching and one non-matching morphed face) and asked to select the matching face as rapidly and accurately as possible. The matching and non-matching faces will be presented either upright or inverted, in various combinations. This task assesses global vs. local visual processing, and it has previously been shown to be abnormal in BDD (Feusner, 2010).

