**3. Visit 3 (Psilocybin Day, Day 0).** The next day, a study psychiatrist again assesses eligibility; those eligible and agreeable receive their dose of psilocybin (25 mg) and spend the next eight hours (longer if needed) with the two therapists; when deemed appropriate, the patient is accompanied home either by a person of their choosing or a staff member. The patient will be reminded that they should not drive or drink alcohol at least until after the end of Visit 4 (next day). Vital signs are taken prior to their dose of psilocybin and prior to leaving the clinic and a study psychiatrist evaluates prior to their departure for whether their condition requires them not to leave. In the latter case, they will either remain in the Biological Studies Unit (BSU) until

cleared by a study psychiatrist or admitted to 5-South inpatient service if they require additional observation overnight.

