### Hospitalization if needed

- Given prior experience with psilocybin treatment, the need for inpatient hospitalization appears unlikely
- In the event that patients require hospitalization they may be admitted to NYSPI 5-South unit.
- Prior to psilocybin dosing [name] will be contacted (email or text [contact]) to ascertain whether backup 5S inpatient bed at NYSPI will be available. In event of lack of availability for such a bed on 5S after it has been offered (e.g., unanticipated issue on inpatient unit) the NYPH. Emergency Room will serve as backup.

**4. Visit 4 (Post-Psilocybin Day 1).** The patient returns to the anxiety clinic and reports any experiences since leaving the clinic as well as having blood, urine, and EKG tests. MRI eligible patients will have another resting state fMRI session, The inverted face task will be repeated.

**5. Visits 5-8 (Post-Psilocybin Weeks 1-3 and 12).** The patient returns 1, 2, 3 and 12 one week later for standard evaluation of psychiatric symptoms, functioning and AE's. These visits may be conducted by phone or secure video.

**6. Telephone visits (Weeks 6 & 9).** The patient is contacted by telephone 6- and 9-weeks post-psilocybin for standard evaluation of psychiatric symptoms and AE's.

**7. Early Withdrawal Visit.** Should the patient or study doctor decide to end the study visits prior to Week 12, if the patient agrees, all Visit 10 (Week 12) ratings including Independent Evaluation will be made.

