### Research Related Delay to Treatment

*Research involving participants who are in need of treatment invariably involves delay to care, and this delay is associated with risk. Scheduling of procedures must be carefully organized to minimize delay. Other delay must involve only that minimally necessary to accomplish the aims of the research while respecting subject well-being and safety. Describe the delay, by virtue of research participation in this study, before a participant can receive treatment of known efficacy or standard care routinely offered in the community.*

Participants in the study will need to be free of SSRI medication for at least 2 weeks prior to psilocybin administration and for 3 weeks thereafter, so total delay to an established treatment will be 5 weeks. Patients who for clinical reasons need treatment intervention sooner will be offered established treatment. If patients need to restart SSRI's prior to the psilocybin session, they will be excluded. If they restart after the session, the reason will be documented, and the patient will be followed until the end of study visit provided that informed consent is maintained.

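### The C-SSRS is scheduled only at screening, Day +1 and Day +84, so no scheduled rating re-applies the suicidality cut-off before dosing and none falls at the five contacts from Day +7 to Day +63

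*Combined protocol and SAP*

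**What the plan says.** In the Schedule of Study Procedures table, the row for the "Columbia Suicide Severity Rating Scale" is marked at the screening visit, Day +1 and Day +84. The Day -1, dosing-day, +7, +14, +21, +42 and +63 cells are blank.

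Exclusion 4 (Inclusion/Exclusion Criteria) rules out current clinically significant suicidality or an attempt in the past year. Its method of ascertainment is "Psychiatric Assessment, MINI, CSSR (items 3 or 4 rated" yes, glossed as active suicidal ideation). Neither the psychiatric assessment nor the MINI is given a cut-off.

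Eligibility is checked again before dosing. For Day -1, Study Procedures says "Eligibility and willingness to participate will be reassessed", and the table's inclusion and exclusion row is marked there. On Day 0 "a study psychiatrist again assesses eligibility". Neither text names a suicidality scale.

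After dosing, the Visits 5-8 text reads "The patient returns 1, 2, 3 and 12 one week later for standard evaluation of psychiatric symptoms, functioning" and adverse events; at weeks 6 and 9 the patient is "contacted by telephone 6- and 9-weeks post-psilocybin for standard evaluation of psychiatric symptoms" and adverse events. The table footnote requires HAM-D, C-SSRS and CGI to be repeated at any visit where the patient reports clinical worsening. Criteria for Early Discontinuation, item 4, asks for the same scales when reported worsening comes with a CGI-Change score above 4. Extra Visits lists, among its triggers, a rise of more than 25% in BDD-YBOCS, significant suicidality (the example being thoughts with any intent) and the physician's judgement.

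Research Related Delay to Treatment says participants must be "free of SSRI medication for at least 2 weeks prior to psilocybin administration and for 3 weeks thereafter". It adds that anyone who clinically needs treatment sooner will be offered it.

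**The concern.** Suicidality can change between screening and dosing. For three other exclusions that can also change, the measuring instrument is repeated on Day -1: the HAM-D (exclusion 1), the urine drug screen (exclusion 3) and the pregnancy test (exclusion 13). The suicidality cut-off is the exception. The MINI, the other instrument named for exclusion 4, is also marked at screening only.

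After dosing, the one instrument aimed at suicidality is absent from every routine contact between Day +1 and Day +84, including the weekly contacts in the planned SSRI-free period.

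Two things are at stake. The first is participant safety: a patient who crosses the stated cut-off after screening, or develops ideation in the weeks after dosing, may not be identified by the scale chosen to define that risk. The second is reporting. Hypothesis 1 is about acceptability, safety and tolerability, and a C-SSRS-based statement under it can describe only the periods that the ratings cover.

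**Working it through.** No sample-size or power formula applies. The check is to read the schedule rows against the day header and count. The header has 11 visit columns, and the four rows below align with it cleanly; the Screening Period column is blank in all four.

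| Scale | Screen | -1 | 0 | +1 | +7 | +14 | +21 | +42 | +63 | +84 |
|---|---|---|---|---|---|---|---|---|---|---|
| C-SSRS | X | | | X | | | | | | X |
| HAM-D | X | X | | X | | | | X | | X |
| MINI | X | | | | | | | | | |
| BDD-YBOCS | X | X | X | X | X | X | X | X | X | X |

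The rows on the table's continuation page (including CGI-Change, adverse events, and inclusion and exclusion criteria) came through text extraction, some with a surplus cell. I use them only for the plain reading that CGI-Change is marked across the post-dose visits and the criteria row at screening and Day -1.

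**Before dosing.** Eligibility rechecks: Day -1 and Day 0. Scheduled C-SSRS at those rechecks: 0 of 2. The screening-to-dose interval is not stated. The blood-sampling section speaks of 4-6 weeks in total, with the last draw three weeks after dosing. That suggests 4 - 3 = 1 to 6 - 3 = 3 weeks, but this is only an inference, and extra screening visits could lengthen it.

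**After dosing.** There are 7 scheduled visits (+1, +7, +14, +21, +42, +63, +84).
- C-SSRS: 2 of 7. HAM-D: 3 of 7. BDD-YBOCS: 7 of 7.
- Neither C-SSRS nor HAM-D: 4 of 7 (+7, +14, +21, +63). This includes all 3 weekly contacts up to Day +21, the end of the 3-week post-dose SSRI-free period.
- Interval between scheduled C-SSRS ratings: 84 - 1 = 83 days.
- If the HAM-D is counted as a partial check, the intervals are 42 - 1 = 41 and 84 - 42 = 42 days.

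**With the scale added.**
- At +7, +14 and +21 only: longest interval 84 - 21 = 63 days.
- At all five contacts: longest interval 21 days (+21 to +42, +42 to +63, +63 to +84).
- Planned post-dose ratings in 12 participants: 2 x 12 = 24 now, 7 x 12 = 84 with all five added.

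**Do the triggers fill the gap?** Take a patient at Day +14 with suicidal ideation but no stated intent, whose BDD is unchanged or better.
- Table footnote: not met unless the patient reports clinical worsening.
- CGI-Change above 4: not met if the global rating is unchanged or improved.
- BDD-YBOCS up by more than 25%: not met. This trigger also leads to an extra visit, with no C-SSRS named.
- Extra visit for suicidality: the example given requires intent. Clinical judgement could still prompt a visit.

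So no trigger need fire, although exclusion 4 describes its own cut-off as active ideation and does not confine it to intent.

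**The case against.** The plan has real safeguards. Before dosing, eligibility is formally reassessed on Day -1, with the criteria row marked, and a psychiatrist reassesses on Day 0. The HAM-D is repeated on Day -1. The footnote on worsening covers any visit, so it applies before dosing too. A reader might infer that a pre-dose C-SSRS happens only if a clinician chooses to do one; that is wrong, because a repeat is mandatory once the patient reports worsening. One could also argue that re-applying exclusion 4 on Day -1 implies repeating its named scale. The table leaves that cell blank, so at best the plan is ambiguous there.

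After dosing, CGI-Change and BDD-YBOCS are clinician-rated at every visit, both with numeric triggers. Adverse events are asked about each time, and each contact includes a standard psychiatric evaluation. Inclusion 6 reads "Currently in psychotherapy (other than CBT for BDD"), so patients also see an outside therapist, and a caregiver, where there is one, is briefed on suicide risk. A reader might infer that suicidality is asked about only informally at these contacts, or that patients are held off SSRIs whatever their condition. The documents support neither: they do not describe the enquiry as informal, and they offer earlier treatment when it is needed.

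Finally, this is a 12-person open pilot that excludes significant current suicidality, a recent attempt, HAM-D above 20 and need for inpatient care. No text in the protocol requires a C-SSRS at every contact.

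All of this stands, and it limits the point to one of scheduling. It does not remove it, because none of these safeguards is a scheduled suicidality rating.

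**Conclusion.** The point holds as a specific, inexpensive improvement to the safety schedule. A scheduled C-SSRS is missing at both pre-dose rechecks and at 5 of 7 post-dose visits, leaving 83 days between scheduled ratings. The practical exposure is narrow: a change before dosing that the patient does not report as worsening, or ideation without intent after dosing in someone whose BDD is stable or improved.

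The documents do not show that suicidality went unmonitored or that anyone was harmed. The continuation report records 12 completers and no serious adverse events. Nor should a reader infer that there was never a suicide risk plan: that section now reads as not applicable because the study is in analysis, so any plan used during enrolment cannot be judged from this text.

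The conclusion assumes that the blank cells mean no routine rating was planned. The C-SSRS version and recall period are not stated. If the Day +84 form looks back over the interval, it may record an earlier event, but too late to act on it. No suicidality endpoint is specified, and a safety statement would also draw on adverse-event data; the limit applies to statements based on the C-SSRS.

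**What to change.** For this design or a successor:
- Mark the C-SSRS on Day -1, or on Day 0 before dosing, and apply exclusion 4's cut-off (items 3 or 4 yes) to that rating.
- Add it at Days +7, +14 and +21 first, then at +42 and +63, by phone or video where the contact is remote.

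Cost at the 10 minutes per rating given under Assessment Instruments, for 12 participants:
- Pre-dose mark only: 1 x 10 x 12 = 120 minutes, or 2 hours.
- Pre-dose plus Days +7, +14 and +21: 4 x 10 x 12 = 480 minutes, or 8 hours.
- All six marks: 6 x 10 x 12 = 720 minutes, or 12 hours.

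No new instrument or visit is needed.

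All participants have completed, so for the present trial only the reporting can change. Report scheduled and triggered C-SSRS results separately, alongside adverse-event data. State the version and recall period used. Limit any C-SSRS-based statement on suicidality to the periods those ratings cover. If a suicide risk plan was in force during enrolment, describe it. None of this needs new data collection.

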## Protocol Summary Form

BDD-REBUS-Q	X		X	X	X	X	X	X	X	X	X	X
Brown Assessment of Beliefs Scale	X		X	X	X	X	X	X	X	X	X	X
Physical Examination	X											
ECG	X				X							
Urinalysis	X		X		X							
Urine for drug/alcohol screening	X		X									
Urine for pregnancy testing*	X		X		X							
Blood for routine laboratory assays	X				X			X				
Vital signs	X		X	X	X							
Height and Weight	X											
PhenX Toolkit Hand Dominance Measure	x											
MRI Metal Screening Questionnaire	x		x		x							
Inclusion & Exclusion Criteria	X		X									
Adverse Events/SAE		X		X	X	X	X	X	X	X	X	X
Resting State fMRI			x		x							
Inverted Face Task			x		x							
Clinical Global Impression - Change					X	X	X	X	X	X	X	X
5Dimension-Altered States of Consciousness				X								
Emotional Breakthrough Inventory					X							
Positive and Negative Affect Schedule			X		X			x	x			
Liebowitz Social Anxiety Scale			x		X				x			X
Psychological Insight Scale					X			X	X			X
Somatomap – 2D Tool			x		x							x
Sheehan Disability Scale			X						x			X
Qualitative Interview				x	x							
Sleep Questionnaire			x		x							
Dysmorphic Concerns Questionnaire			x		x			X	X			x

At any visits in which patient reports clinical worsening, HamD, CSSR, and CGI will be repeated.

### Criteria for Early Discontinuation

Define criteria that will be used to exit or drop subjects from the study and operationalize. Indicate the time points when such criteria will be applied, and describe the rating instruments, parameters, and thresholds that will lead to a decision

*to terminate a subject's participation and the role of the person who will make these determinations. Studies which include a medication taper and discontinuation may be asked to include an independent medical monitor (an MD not on the study team) who will aid the study team in determining whether study discontinuation is needed. In addition, explain procedures for managing subjects who are withdrawn from the protocol.*

*For treatment studies: To minimize risks to subjects, operationalized drop-out criteria should be defined so that subjects who worsen, or in some cases, fail to improve, are removed from the study and offered standard care. The threshold for drop-out should consider the level of risk associated with non-improvement for the specific disorder, the availability of alternatives, and the typical required duration of treatment. For example, emergence of suicidal intent, or psychosis, should prompt immediate clinical evaluation and withdrawal from the study.*

1. Patient withdraws consent
2. Study personnel determines it is not in the patient's best interest to continue in the study.
3. Clinical worsening
4. At each assessment participants will be evaluated for clinical worsening, and any participant who reports symptomatic worsening (CGI Change Score >4) will be further evaluated for need for urgent clinical treatment. Further evaluation will include the Hamilton Depression Scale, the Columbia Suicide Severity Rating Scale (C-SSRS), and the Clinical Global Impression Change Scale, but the ultimate decision to provide or refer to non-study treatment will be based on clinical judgement, with reasoning documented in the chart.
5. Any participant who evidences need for non-study clinical treatment before psilocybin administration will be removed from the study and offered appropriate referrals, including transitional treatment in the Anxiety Disorders Clinic, or being walked to the emergency room if indicated. After psilocybin administration, clinical deterioration will be treated the same way, except that patients will be permitted to continue participation in remaining study assessments.
6. Potential pregnancy: Participants who prior to dosing have a positive pregnancy test or report suspecting pregnancy will be removed from the study. Participants who after dosing have a positive pregnancy test will be excluded from the repeat MRI but will be allowed to continue in study assessments of symptoms. They will be offered assistance with obstetrical follow-up

